## 6.0. Intervention methodology

### 6.1 Combining Stepping Stones and Creating Futures:

The **purpose** of the combined intervention is to both provide the necessary skills for strengthening relationships and building gender equity for women and men which are essential for IPV prevention, and provide a means of alleviating the grinding poverty which poses a barrier to women's ability to use informational and attitudinal empowerment skills and messages.

The **intervention methodology** will include a total of 21 sessions: 10 sessions of Stepping Stones delivered before 11 sessions of Creating Futures. Sessions are all approximately three hours long and are delivered twice a week, over approximately 12 weeks. Both interventions are delivered primarily to single sex groups of about 20 people and use a similar participatory methodology.

The key sessions of Stepping Stones cover: gender and peer influences our actions; sex and love; conception and contraception; STIs and HIV; safer sex and condoms; GBV; motivations for behaviour (including influences of alcohol and poverty); and communication skills.

The key sessions of Creating Futures cover: my life and the resources I have used in my life and livelihood, setting medium term livelihood goals and the need for assets for livelihoods and coping with crises; social resources for livelihoods (trust and community participation); education and learning including past experiences and how to build on these; getting and keeping jobs including work expectations and how ones on own behaviours may impede or increase our ability to get a job and to keep it, appropriate work opportunities and increase owns own ability to market ones skills and apply for work and overcome challenges in job

seeking and maintaining a job; income generating activities and how to identify viable business opportunities, the resources necessary to respond to such opportunities, basic business principles and business risks; saving and coping with shocks including spending patterns and strategies for saving, and causes and consequences of getting into debt and ways of overcoming debt.

None of these could substantially affect the outcomes of the intervention. A major criteria is that participants have sought treatment/support extensively through the current systems. Moreover, given a duty of care to participants established during the trial these low levels of support provide a way of the team providing relatively little inputs, which have major impacts.

The relief fund will be overseen by three team members and will adhere to all financial reporting and auditing requirements. Each ‘use’ of the relief fund will be recorded and documented for future review.

### 6.3 Pilot research and field testing

The SS CF combined intervention was piloted among young adults in Durban informal settlements in 2012-13. 123 women and 110 men were recruited and interviewed on two occasions and then invited to participate in the intervention. They were then followed up 6 months later and 12 months later. Overall retention at 12 months in the study was 88%. Data suggests that attendance at sessions was approximately 60%.

The results of the pilot were assessed in long term qualitative research and observational research and have been published [49-52]. The analysis showed that men's mean earnings in the past month increased by 247% from R411 (~\$40) to R1015 (~\$102, and women's by 278% R 174 (~\$17) to R 484 (about \$48) (trend test,  $p < 0.0001$ ). There was a significant reduction in women's experience of the combined measure of physical and/or sexual IPV in the prior three months from 30.3% to 18.9% ( $p = 0.037$ ). Both men and women scored significantly better on gender attitudes and men significantly reduced their controlling practices in their relationship. The prevalence of moderate or severe depression symptomatology among men and suicidal thoughts decreased significantly ( $p < 0.0001$  and  $p = 0.01$ ) [13].

## 7.0 Study methods

### 7.1 Objective of the RCT

- i) The **primary objective** is to determine the effectiveness of the combined intervention in reducing IPV experience in women and perpetration by men, including reducing controlling behaviours.
- ii) The **secondary objective** is to determine the impact of the combined intervention in strengthening livelihood seeking activities, improving mental health reducing sexual risk taking and reducing participation in crime due to lack of money.

### 7.2 Study design

The study is a randomised controlled trial with two arms:

1. Stepping Stones and Creating Futures
2. Control communities (cash incentive for study participation and delayed intervention)

The control arm will be given a cash incentive for study participation which is large enough to incentivise participation in interviews in the absence of an intervention over the two years prior to them being offered the intervention.

### 7.3 Setting

The study is set in informal settlements in and around eThekweni (Durban).

### 7.4 Cluster Definition/Inclusion

A cluster will be defined as a discrete urban informal settlement.

Eligibility criteria for informal settlements:

- \* Informal settlements in the eThekweni Municipality.
- \* Informality is defined by not having formal service provision within the home e.g. no electricity legally supplied, and no piped water to housing.
- \* Project Empower have assessed that it is safe to work in these communities

Another criteria – although hard to ‘enforce’ or assess is that no large development/intervention studies or programmes are identified at recruitment into the intervention

The nature of urban informal settlements in eThekweni is such that they are typically discretely geographically bounded; in essence they tend to be in clearly defined spaces. The variation in size of informal settlements is dealt with in three primary ways:

- 1) Small informal settlements close to each other will be clustered together to form a larger informal settlement cluster where we can recruit n=40 participants
- 2) Large informal settlements, if possible, will be split into separate clusters using naturally occurring boundaries and space to limit the potential for contamination (although this is a minor issue in this study as it is group-based)
- 3) In analyses we will account for variation in baseline characteristics of clusters – although there is nothing to suggest that size of informal settlement will vary measured characteristics

Clusters will be identified using a list of urban informal settlements provided by the Municipality. These name and provide basic information about all informal settlements in eThekweni, including location and approximate number of residential dwellings. While contamination is a concern, as it is a group intervention – rather than community mobilisation – spill over effects are likely to be minimal.

Given the challenging nature of working in urban informal settlements we will identify clusters based on pragmatic decisions around security and safety.

### **7.5 Inclusion criteria**

Participants must be normally resident in an informal settlement, aged 18-30 years, not in formal employment, able to communicate in the main languages of the study (isiXhosa or isiZulu) and not suffering from a mental deficit (learning difficulty, mental illness or substance abuse) which would impair their ability to consent to participation in the trial.

Our age grouping is based on the requirement that participants provide informed consent, those under 18 cannot do so and require parental consent to participate, which may be challenging in informal settlements where young people do not live with their parents. Our pilot data suggests that an upper-age limit of 30 is reasonable; while the majority of participants are under 25, a significant minority were older and faced similar life challenges.

### **7.6 Randomisation and blinding to study arm**

Randomisation will be undertaken by cluster after clusters have agreed to participate in the study. Community gate keepers will provide permission to work in a cluster/informal settlement (see 9.1 below). Clusters thereafter will not be blind to their study arm.

All clusters will be allocated numbers and the randomisation will be performed by [name], MRC biostatistician, using a system of numbers. At the time of randomisation she will not know which number is allocated to which cluster. We are not doing public randomisation because of political sensitivities and that clusters are within wards, rather than wards themselves.

## 7.7 Sample size and sample size calculation

There will be 17 clusters in each of the two study arms.

### 7.7.1 Sample size calculation:

In the pilot study conducted in 2012-13 the past year prevalence of physical and/or sexual IPV perpetration and victimisation was 45% among men and 41% among women. These levels of violence are exceptionally high by South African standards, so we have modelled the sample size on a range of possible baseline rates (see the table). The sample size assumes 14 will be followed up per cluster (of the 20), but figures are robust to a follow up of only 12 in each cluster. Assuming a coefficient of variation  $k=0.2$  and modelling 80% power. The table shows that with 14 male (and 14 female) participants per cluster and 16 clusters we will have power to detect a range of possible incidence and impact scenarios and to analyse men and women separately (see table). Our power will be further enhanced by having multiple assessments and an additional two clusters.

IPV incidence (12 months)			# of clusters required by arm
11	12	power	
36	29	80	16
45	36	80	15
41	33	80	16
24	19	80	14
18	14	80	13
30	24	80	15

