## **METHODS:**

*Design:* A randomised controlled trial with two arms

- i) Stepping Stones and Creating Futures
- ii) Control arm (Cash incentive for study participation and delayed intervention)

*Interventions:* There are two interventions which will be delivered sequentially:

i) Stepping Stones which consists of 10 sessions of about 3 hours duration. This is a participatory intervention which is delivered in the main to single sex groups of about 20 people. It seeks to strengthen relationships and to transform views on gender and in the process impact on exposure to, or participation in, gender-based violence and HIV risk. These cover gender and peer influences our actions; sex and love; conception and contraception; STIs and HIV; safer sex and condoms; GBV; motivations for behaviour (including influences of alcohol and poverty); and communication skills.

ii) Creating Futures is a facilitated group intervention covering eleven, three-hour sessions in single-sex groups of approximately twenty people. The key sessions cover: my life and the resources I have used in my life and livelihood, setting medium term livelihood goals and the need for assets for livelihoods and coping with crises; social resources for livelihoods (trust and community participation); education and learning including past experiences and how to build on these; getting and keeping jobs including work expectations and how ones on own behaviours may impede or increase our ability to get a job and to keep it, appropriate work opportunities and increase owns own ability to market ones skills and apply for work and overcome challenges in job seeking and maintaining a job; income generating activities and how to identify viable business opportunities, the resources necessary to respond to such opportunities, basic business principles and business risks; saving and coping with shocks including spending patterns and strategies for saving, and causes and consequences of getting into debt and ways of overcoming debt.

*Setting:* Informal settlements in and around EThekweni Municipality (Durban)

*Sample size:* 1320 adults (40 per cluster – 20 male and 20 female) will be recruited in 34 clusters for the study. In each cluster will be based in an informal settlement.

*Integrated qualitative research study:* A multi-method qualitative evaluation of the intervention will take place, comprising of 40 repeat in-depth interviews (20 women, 20

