## **11.0 Challenges**

We recognise that attendance at the intervention will be voluntary, the intervention is long and it is difficult to know exactly what the level of sustained participation will be. We will collect data on attendance so that we can use this information in the data analysis. In the pilot study we found approximately 60% of sessions were attended, and this showed promise of impact. We do not expect attendance to be lower than in the pilot. We also may encounter loss to follow up. We have inflated the necessary sample size to allow for a possible 40% loss to follow up without critical loss of power for the evaluation. Retention of participants is always a challenge in cohorts and plans for this are outlined below.

Informal settlements are tricky areas to work in because they can be dangerous for staff and also sometimes have quite complex local politics. Project Empower has been working in informal settlements in Durban since it was established 13 years ago and so we are confident that they have the necessary understanding of the issues in these areas to be able to undertake the mobilisation for the study and intervention safely.

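### The sample-size table reproduces only if incidence percentages are entered as whole numbers; on the correct scale, 16 clusters per arm give about 18–36% power, not 80%.

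*Protocol*

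**What the plan says.** Protocol 7.7.1 takes the pilot's past-year prevalence of physical and/or sexual IPV, which "was 45% among men and 41% among women". Because those levels are unusually high, it adds lower ones: "so we have modelled the sample size on a range of possible baseline rates". The table lists six pairs of 12-month incidence (36/29, 45/36, 41/33, 24/19, 18/14, 30/24) and gives 16, 15, 16, 14, 13 and 15 clusters per arm for 80% power. The stated inputs are a between-cluster coefficient of variation of 0.2 and 14 people followed per sex per cluster, out of 20 recruited. No formula, alpha or sidedness is given.

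Four claims rest on the table:
- Power is adequate for each sex: "with 14 male (and 14 female) participants per cluster and 16 clusters we will have power to detect a range of possible incidence".
- Attrition hardly matters: "figures are robust to a follow up of only 12 in each cluster".
- There is something in reserve: "Our power will be further enhanced by having multiple assessments and an additional two clusters".
- Protocol 11.0 (Challenges) adds: "We have inflated the necessary sample size to allow for a possible 40% loss to follow up without critical loss of power".

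Protocol 7.7 plans 17 clusters per arm. SAP 2.1 refers the reader back to the protocol for the sample-size calculation and does not revisit it.

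**The concern.** The table behaves in a way that a calculation for a binary outcome in small clusters should not. Every row is a relative reduction of about 20% (19% to 22%), yet the table asks for fewer clusters when the outcome is rarer: 13 at 18%, against 16 at 36%. With only 14 people per cluster, a rarer outcome at the same relative reduction should need more. The figures also barely respond to cluster size, although binomial sampling error should dominate at 14 per cluster. Both features suggest that the within-cluster term has almost dropped out.

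If so, the 80% promised separately for men and women is not there. A true 20% reduction would more likely be missed than found, and a non-significant result would be read as coming from an adequately powered trial.

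**Working it through.** **Inputs.** From Protocol 7.7.1: the six pairs, k = 0.2, 80% power, 14 followed per sex per cluster (12 in the robustness statement). From Protocol 7.7: 17 clusters per arm. From SAP 3.2: two-sided 5%. So (1.96 + 0.84)² = 7.849. The 45 and 41 in the table are the pilot percentages quoted just above it, so the entries are percentages over 12 months.

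**Step 1: reproduce the table.** The standard formula for unmatched cluster rates is

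c = 1 + 7.849 × [(λ₁ + λ₂)/y + k²(λ₁² + λ₂²)] / (λ₁ − λ₂)²

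Row 36/29 with whole numbers and y = 14: the within-cluster term is 65/14 = 4.64, the between-cluster term is 0.04 × (1296 + 841) = 85.48, and the squared difference is 49. So c = 1 + 7.849 × 90.12/49 = 15.44, which rounds up to 16.

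| Pair | y = 14 | y = 12 | Table |
|---|---|---|---|
| 36/29 | 15.44 | 15.56 | 16 |
| 45/36 | 14.43 | 14.53 | 15 |
| 41/33 | 15.24 | 15.34 | 16 |
| 24/19 | 13.73 | 13.89 | 14 |
| 18/14 | 12.32 | 12.51 | 13 |
| 30/24 | 14.71 | 14.85 | 15 |

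All six rows match. At y = 12 the values round up to the same integers, which accounts for the statement about 12 per cluster.

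**Step 2: why the scale matters.** The within-cluster term is linear in λ and the between-cluster term is quadratic. Entering 36 for 0.36 multiplies the first by 100 and the second by 10,000. In row 36/29 the ratio of within to between is 4.64/85.48 = 0.054 as entered, but 0.0464/0.00855 = 5.43 on the rate scale. The limit for infinitely large clusters is 11.2–14.7 per arm, close to the table.

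**Step 3: correct scale.** For proportions, [p₁(1−p₁) + p₂(1−p₂)]/m replaces (λ₁ + λ₂)/y. Row 36/29 with m = 14: (0.2304 + 0.2059)/14 = 0.03116. Adding 0.00855 gives 0.03971. Then c = 1 + 7.849 × 0.03971/0.0049 = 64.6, or 65 per arm.

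Power with c clusters per arm is Φ(√[(c − 1)(p₁ − p₂)²/V] − 1.96), where V is the bracketed variance. For this row with c = 16: √(15 × 0.0049/0.03971) = 1.36, and Φ(−0.60) = 27.4%.

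| Pair | Clusters per arm needed (m = 14) | Power, 16 per arm | Power, 17 per arm | Power, 17 per arm, m = 12 |
|---|---|---|---|---|
| 36/29 | 65 | 27.4% | 29% | 26% |
| 45/36 | 47 | 36.0% | 38% | 35% |
| 41/33 | 56 | 31.4% | 33% | 30% |
| 24/19 | 89 | 21.2% | 22% | 20% |
| 18/14 | 106 | 18.5% | 19% | 18% |
| 30/24 | 75 | 24.2% | 26% | 23% |

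The person-year rate formula on the correct scale (y = 14) is less favourable: 70–124 clusters per arm, and 17–27% power with 17.

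**Step 4: favourable readings.**
- All 20 retained, 17 per arm: 25–46%.
- Two years of person-time (y = 28, rate formula), 17 per arm: 28–42%, with 42–68 clusters needed.
- Clustering ignored, 16 × 14 = 224 per arm: 21–49%.
- One-sided test with k = 0, m = 14: still 28–75 clusters per arm.

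**Step 5: what 17 per arm can detect** with 80% power, m = 14 and k = 0.2: 45% to 30%, 41% to 27%, 36% to 23%, 30% to 18%, 24% to 13%, 18% to 9%. These are relative reductions of 33% to 52%.

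**The case against.** The mechanism is inferred. The protocol names no formula, alpha or sidedness, and the table's column labels are damaged in the extracted text. That is fair, and it is why the point is worded as a table that reproduces only under whole-number entry. The shortfall in power does not depend on how the error arose.

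The gain from repeated assessments cannot be dismissed from the SAP alone. The Poisson analysis in Protocol 10.2 counts person-years from baseline to first report, and SAP 3.5.3 adds a model for 12 and 24 months. This also stands in part. The gain is unquantified, and it does not apply to the SAP primary outcomes, all of which are set at 24 months. Protocol 10.2 likewise defines the incident case at 24 months. Crediting two full years still gives at most 42%.

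Falling from 14 to 12 per cluster costs only about 1 to 4 percentage points. True: the error lies in the base power, not in that step. But the 40% loss in Protocol 11.0 is a fall from 20 to 12, which takes row 36/29 from 36% to 26%, so that sentence also fails.

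Baseline covariates may add precision. They may, but neither document quantifies the gain.

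Finally, recruitment is over (680 women and 677 men, SAP 2.1), and the SAP promises confidence intervals, which would show the imprecision. The correction is therefore one of disclosure and interpretation. It still matters, because the protocol expressly claims adequate power for each sex.

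**Conclusion.** The concern holds. The table is on the wrong scale, and with the plan's own inputs the stated 80% is 18–36% at 16 clusters per arm and 19–38% at the planned 17. This rests on three assumptions: two-sided 5% from the SAP, table entries as percentages over 12 months, and 14 people per cluster in each sex-specific analysis. No favourable variant on the correct scale approaches 80%.

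The figures apply to combined physical and/or sexual IPV, the protocol's primary outcome. SAP 2.5.1 replaces it with physical, sexual and severe IPV separately. Each is a subset of the combined measure and so cannot be more common. At the same relative reduction and k, power for them can be no higher than for the combined measure.

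**What to change.** 1. Recompute the table in Protocol 7.7.1 with incidence as proportions, or as rates per person-year if the Poisson analysis is kept. State the formula, alpha and sidedness.
2. Replace the 80% claim with the power of 17 clusters per arm and 14 per cluster (19–38% on the proportion scale), and give the detectable effect, for example 41% to about 27%.
3. Delete the statement on robustness to 12 per cluster, and the statement in Protocol 11.0 on tolerating 40% loss.
4. Say that any gain from repeated assessments is unquantified and does not apply to the SAP's 24-month primary analysis.
5. Add a sentence to the SAP giving the corrected power for combined physical and/or sexual IPV. Say that it does not carry over directly to the separate IPV outcomes, and that a non-significant result must be read against it through the confidence interval.
6. As a separate clerical point, reconcile "1320 adults (40 per cluster" in the executive summary with 34 clusters: 34 × 40 = 1360.

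The cost is a corrected table and a few sentences. No participants are added; the stated power becomes less favourable.

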## 7.8 Study's main outcomes

### *Primary outcome:*

The past year incidence of IPV (perpetration of physical and/or sexual IPV for men and victimisation for women), including change in controlling behaviour.

### **Secondary outcomes**

gender attitudes (more equitable)  
depression (past week)

suicidal thoughts in the past month  
 quarrelling in last 12 months over drinking  
 problem drinking  
 last sex with main partner  
 transactional sex in last 3 months  
 condom use on last sex  
 mean earnings in last month  
 stole in the last month due to lack of money for food

**Tertiary outcomes: other livelihood strengthening outcomes**

Frequency of livelihood strengthening efforts  
 Work stress mean score  
 Feelings about work situation mean score  
 Receiving a grant  
 Crime participation score  
 Very difficult to find R 200 in an emergency

**7.8 Questionnaire for main outcome assessment**

The primary and secondary outcomes will be measured using a standard questionnaire. Separate male and female questionnaires are available for baseline (Appendix 01 – male; Appendix 02 – female) and 12 and 24 months (Appendix 03 – male; Appendix 04 – female).

The primary outcome for women will be assessed using standard measures developed by the World Health Organisation for its multi-country study [53] and for men those developed and tested in the UN multi-country study on men and violence [54]. These have been tested in South Africa over many years in different populations and most recently used in the pilot of Stepping Stones and Creating Futures (SS CF pilot) [49].

The background variables, secondary outcomes measures and other outcomes were used in South Africa in the SS CF pilot and elsewhere by the Gender & Health Research Unit (and others). The questionnaire, and its translations, will be largely the one used in the pilot.

Measures for Secondary outcomes	
gender attitudes (more equitable)	GEMS adapted for South Africa
depression (past week)	CES-D
suicidal thoughts in the past month	CES-D
quarrelling in last 12 months over drinking	One item – from AUDIT
problem drinking	AUDIT
last sex with main partner	Single item – used in pilot
transactional sex in last 3 months	Measured using scale derived from Dunkle et al 2004
condom use on last sex	Single item – used in pilot
mean earnings in last month	Single item– used in pilot
stole in the last month due to lack of money for food	Single item– used in pilot

